### 5. GENERAL STATISTICAL METHODS

### **5.1.** Sample Size Justification

The planned total enrollment for the study is approximately 30 patients.

Twenty-four patients will yield 90% power to detect a treatment difference of 37% at a 2-sided 5% significance level assuming the mean percent reduction from baseline to Month 6 in 24-hour urinary oxalate corrected for BSA is 17% with a standard deviation (SD) of 25% in the placebo arm, and a mean percent reduction from baseline to Month 6 in 24-hour urinary oxalate corrected for BSA of 54% with SD of 25% in the lumasiran arm.

### **5.2.** General Methods

Continuous data will be described using descriptive statistics such as the number of observations (n), mean, standard deviation, standard error, median, quartiles, minimum, and maximum. For the summary statistics of all numerical variables unless otherwise specified, minimum and maximum will be displayed to the same level of precision as reported. Median and mean will be presented to the level of precision collected in database plus one additional decimal. Standard deviation and standard error will be presented to the level of precision collected in the database plus 2 additional decimals.

For assessments with repeated collections at a given study visit (e.g. ECG parameters, height for ages<18 years old), the mean will represent the value at the visit for all parameters except for 24-hour urine PD parameters. For 24-hour urine PD parameters, if there are any repeated collections at a visit, then the median will represent the value at that visit. For biomarker and/or lab data, if any value is recorded as <lower limit of quantification (LLOQ) then the assigned value used for calculations of summary statistics will be assigned a value of the LLOQ.

Categorical and ordinal data will be described using the patient count and percentages in each category. When count data are presented, the percentage will not be presented when the count is zero.

Tables and figures will primarily summarize data during the double-blind period and during lumasiran treatment. These time periods are defined directly below. In addition, there will be a subset of tables and figures for efficacy endpoints which will also summarize by protocol defined study visit across the entire study for patients in the FAS set.

**During the Double-Blind (DB) Period:** defined as the time period prior to the first study drug dose date/time in the extension period (e.g. date/time of lumasiran dose at month 6).

Tables and figures will be presented by treatment arm (lumasiran or placebo). For safety summaries (i.e. AEs, Labs, ECGs, VS, etc.), all assessments up to the date/time of the first dose in the extension period (i.e. date/time of lumasiran at month 6) or, for patients not dosed in the extension period, all assessments collected within 84 days of the last dose of study drug will be included. For efficacy summaries, all data up to and including the month 6 visit will be presented.

**Extension Period**: defined as the period starting on/after the first date/time of lumasiran at month 6 (i.e. start of the 3-month blinded treatment extension period).

**During Lumasiran treatment:** defined as the time period during which patients receive lumasiran (i.e. on or after the first date/time of lumasiran until 84 days after the last dose of lumasiran). Baseline and study days will be relative to the first dose of lumasiran and will be rederived for patients initially randomized to placebo (Section 5.4 and Section 5.8).

Summary tables and figures will be presented by treatment sequence (lumasiran/lumasiran, placebo/lumasiran and all lumasiran treated). Both safety and efficacy summaries will include all assessments during lumasiran treatment (i.e. any assessment collected on or after the first dose until 84 days after the last dose of lumasiran).

Per-patient listings will include all data collected during the entire study. The listings will be sorted by randomized arm. Within patient, there will be a variable to indicate the period of the data collection.

Day 1 will be defined as the day of the first dose of study drug (lumasiran or placebo). Day is relative to first dose date of study drug for all patients:

If the assessment date is after the date of first study drug dose, then the study day will be calculated as:

Study Day = Date of assessment – date of first dose of study drug + 1

If assessment date is before the date of the first dose of study drug, then study day will be calculated as:

Study Day = Date of assessment – date of first dose of study drug

For patients who were randomized to placebo but later received lumasiran, these patients will have additional variables displayed in listings to reflect the data collected relative to the first dose of lumasiran. At a minimum, all listings will include two sets of definitions for the following variables:

- Baseline: relative to first randomized dose of placebo and relative to first dose of lumasiran (Section 5.4).
- Study Day: relative to first randomized dose of placebo and relative to first dose of lumasiran.
- Visit: based upon actual study visits and visits re-aligned relative to first dose of lumasiran (Section 5.8).

Formal statistical hypothesis testing will be performed on the primary and secondary efficacy endpoints evaluated during the DB period (except eGFR as this endpoint is not expected to change within six months). Testing will be conducted at the nominal 2-sided 0.05 level of significance. Secondary endpoints will be tested in a prespecified hierarchy (Section 5.6). Summary statistics will be presented, as well as 2-sided 95% confidence intervals on selected parameters, as described in the sections below.

All data recorded on the CRF will be displayed in data listings.

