Study Day (±Visit Window)	Note	337 (±28)	421 (±28)	505 (±28)	589 (±28)	673 (±28)	757 (±28)	Every 168 days (±28)	1597 (±28)	1681 (±28)	Every 84 days (±28)
Study drug administration	Study drug to be administered every 3 months through M57. Dosage is based on total body weight. See Section 5.2.2.	X	X	X	X	X	X	X (every 84 [±28] days)	X		
Blood samples for PK analyses	See Table 3. For East Asian sites, see Table 4.	X									
Urine samples for PK analyses	Patients at East Asian sites only; see Table 5.	X									
Blood sample for PD analyses		X	X	X	X	X		X		X	X
≥3 separate 24-hour urine collection for PD analyses	≥2 collections must be valid. Collect within 14 days prior to dosing. See Section 6.3.1 and Table 7 for details.	X									
Single 24-hour urine collection for PD analyses	Collect within 14 days prior to dosing or visit. If invalid, should be repeated. See Section 6.3.1 and Table 7.		X	X	X	X		X		X	X
Random urine sample for PD analysis	See Section 6.3.1 and Section 6.3.1.2.	X	X	X	X	X		X		X	X
Blood sample for pyridoxine (vitamin B6) levels	Only if taking pyridoxine for the treatment of PH1. To be collected ≥6 hours from last dose of pyridoxine. See Section 5.3.	X	X	X							
Renal stone events	See Section 6.3.3.	Continuous									

Study Period	Open-Label Extension Period									Safety Follow-up (Patients who Discontinue Treatment)
	Through Year 2						Through Year 5			
Study Visit	M12	M15	M18	M21	M24	M27	M30; M36; M42; M48; M54	EOT M57	EOS/ET M60	
Study Day (±Visit Window)	337 (±28)	421 (±28)	505 (±28)	589 (±28)	673 (±28)	757 (±28)	Every 168 days (±28)	1597 (±28)	1681 (±28)	Every 84 days (±28)
Renal ultrasound	See Section 6.5.5.	X				X	X (M36 and M48 only)		X	
Quality of life questionnaires	See Section 6.7.	X		X		X	X		X	
Patient and caregiver experience surveys	See Section 6.8.	X		X		X	X		X	
Patient and caregiver impact questionnaire	See Section 6.9.	X		X		X	X		X	
Healthcare resource utilization	See Section 6.10.	Continuous								
Antidrug antibody sample		X		X		X	X		X	X
Blood and urine samples for exploratory analyses	See Section 6.6.	X		X		X	X		X	
Review/record adverse events	See Section 6.5.7.2.	Continuous								
Prior and concomitant medications	See Section 5.3.	Continuous								

Abbreviations: ECG=electrocardiogram; EOS=end of study; EOT=end of treatment; ET=early termination; M=month; PD=pharmacodynamic; PH1=primary hyperoxaluria type 1; PK=pharmacokinetic; WOCBP=women of child-bearing potential.

Notes:

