- Assessments are to be performed prior to dosing, where applicable. When applicable, pregnancy test results must be known prior to dosing. When scheduled at the same time points and where feasible, the assessments of vital signs and 12-lead ECGs should be performed before physical examinations, and blood sample collections.
- Visits and study drug dosing may be conducted offsite where applicable country and local regulations and infrastructure allow (at the discretion of the Investigator, based on safety and tolerability), provided the patient has tolerated a dose of lumasiran administered in the clinic. If a visit is conducted offsite, a body system assessment may be performed in lieu of a physical examination.
- Study drug is administered once every 3 months throughout the open-label extension period.

- See Section 4.3.1 for instructions for patients who discontinue study drug.
- In situations where a study visit is unable to be completed (either at the site or offsite by a healthcare professional), the Investigator (or delegate) will verbally contact the patient within the study visit window to assess concomitant medications, renal stone events, adverse events, and healthcare utilization.
- Gray-shaded column indicates the visit where assessments span 2 days.

Table 3: Pharmacokinetic and ECG Assessment Time Points: All Sites except East Asian Sites

Study Month/ Study Day	Sampling Time (hh:mm)	Blood PK Sample	ECG
Screening	Any time during visit		X ^a
Month 0 (Day 1)	Predose	X	X ^b
	04:00 (±1 hour)	X	X ^b
	24:00 (±2 hours)	X	
Month 3 (Day 85± 4 days)	Predose	X	X ^a
	04:00 (±1 hour)	X	
Month 6 (Day 169±7 days)	Predose	X	X ^b
	04:00 (±1 hour)	X	X ^b
	24:00 (±2 hours)	X	
Month 9 (Day 253±4 days)	Predose	X	X ^a
	04:00 (±1 hour)	X	
Month 12 (Day 337±28 days)	Predose	X	X ^a
	04:00 (±1 hour)	X	
	24:00 (±2 hours)	X	
Months 24, 36, 48, 60 (see Table 2)	Predose		X ^a

Abbreviations: ECG=electrocardiogram; hh:mm=hour:minute; PK=pharmacokinetics

Notes:

- Predose samples are collected on the day of dosing.
- The hour (±range) indicate sample collection timing relative to dosing. Precise PK sample times (hour and minute) are recorded. See Section 7.2.7 for additional information on PK assessments.

- Patients should be supine for at least 10 minutes before each ECG is obtained. See Section 6.5.4 for additional information on ECG assessments.

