- Patients who had been randomized to lumasiran will be given 3.0 mg/kg lumasiran at Month 6 and placebo at Months 7 and 8
- All patients will be given a maintenance dose of lumasiran at Month 9 and then once every 3 months thereafter

Assessments of efficacy and safety will be conducted during visits to the clinical study center every 2 weeks for the first month of this part of the study and monthly thereafter through Month 9.

Patients will receive their first open-label dose of lumasiran at Month 9 to begin their participation in the open-label extension (OLE) part of the study, in which they will be treated with lumasiran administered once every 3 months for up to 48 months; patients will receive their last dose of lumasiran at Month 57. Patients entering the OLE period will undergo efficacy and safety assessments every 3 months through Month 24, and every 6 months until the end of study (EOS) visit at Month 60.

24-hour urine collections will be performed for evaluation of oxalate excretion. At the Month 6 and Month 12 visits, patients will provide at least three 24-hour urine collections and ≥ 2 of these collections must be valid (see Section 6.3.1.1) prior to completion of the Month 6 and Month 12 visit assessments. Single 24-hour urine collections will be obtained for the study visits specified in the Schedules of Assessments. Details on 24-hour urine collection procedures are included in Section 6.3.1.

An external, independent DMC will monitor safety over the course of the study. Details for the committee will be provided in DMC charter.

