The primary change occurs in Table 2, Schedule of Assessments; Schedule of Assessments – Open Label Extension Period (After Month 9 through Year 5).

Revised text: In Table 2, the visit window was changed to ± 28 days (previously ± 14 days) for all visits.

Section also reflecting this change:

- Table 3, Pharmacokinetic and ECG Assessment Time Points: All Sites except East Asian Sites, Footnote Notes

Purpose: Expand study assessment windows for ECGs and renal ultrasound.

The primary change occurs in Section 6.5.4, Electrocardiogram

Revised text: **During periods of time when the COVID-19 pandemic impedes the ability of patients to travel to the study site, ECG assessments may be completed up to 7 months after the intended timepoint for visits at Month 12 and later.**

Sections also reflecting this change:

- Table 3, Pharmacokinetic and ECG Assessment Time Points: All Sites except East Asian Sites, Footnote Notes
- Section 6.5.5, Renal Ultrasound

Purpose: *Expand the window for completion of QOL questionnaires, patient and caregiver experience surveys and patient and caregiver impact questionnaires.*

The primary change occurs in Section 6.7, Quality of Life (QOL) Questionnaires

Revised text: **During periods of time when the COVID-19 pandemic impedes the ability of patients to travel to the study site, the KDQOL, PedsQL, and the EQ-5D questionnaires can be completed up to 4 months after the intended time point.**

Sections also reflecting this change:

- Section 6.8, Patient and Caregiver Experience Survey
- Section 6.9, Patient and Caregiver Impact Questionnaire

Purpose: *Reduce required blood sample collection timepoints for PK assessments.*

The primary change occurs in Table 3, Pharmacokinetic and ECG Assessment Time Points: All Sites except East Asian Sites, Footnote Notes.

Revised text: **Blood samples for PK assessment may be collected at 24 hours postdose as feasible during periods of time when the COVID-19 pandemic impedes the ability of patients to travel to the study site and the healthcare professionals to go to the patients' homes.**

Purpose: *Allow continual assessments of AEs, concomitant medication use, renal stone events, and healthcare utilization via remote contact.*

The primary change occurs in Table 1 and Table 2, Schedules of Assessments

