### 1. INTRODUCTION

Primary hyperoxaluria type 1 (PH1) is a rare autosomal recessive disease characterized by excessive oxalate production by the liver and consequent hyperoxaluria. PH1 is caused by mutations in the alanine glyoxylate aminotransferase (AGXT) gene, which encodes the liver peroxisomal enzyme alanine-glyoxylate aminotransferase (AGT). As a consequence of AGT deficiency, glyoxylate accumulates and is oxidized to oxalate in the hepatocyte and ultimately transported to the kidneys for excretion. Oxalate, in the form of its calcium salt, is excreted almost entirely by the kidney. Due to its insolubility, calcium oxalate can crystallize readily in the urinary tract. In PH1, excess urinary oxalate results in recurrent nephrolithiasis and/or nephrocalcinosis, which can lead to pain, infections, progressive kidney disease and failure, along with reduced quality of life.[Cochat 2013] As renal function declines, elimination of oxalate is further reduced, such that calcium oxalate accumulates in bone, vasculature, skin, retina, heart, and nervous system, resulting in severe end-organ damage.[Cochat 2013] This devastating condition, systemic oxalosis, arises when the estimated glomerular filtration rate (eGFR) has declined to below 30 to 45 mL/min/1.73 m².[Cochat 2013]

The ILLUMINATE-A Study (ALN-GO1-003) is a Phase 3 study designed to evaluate the efficacy and safety of SC-administered lumasiran in patients with PH1. This statistical analysis plan (SAP) has been developed based on the protocol of the ILLUMINATE-A study (Amendment 2 dated 19 March 2019).

The analysis methods described in the protocol may be updated in this statistical analysis plan (SAP). Any change to the data analysis methods described in the protocol, as well as the justification for the change, will be described in this SAP (Section 8) and the clinical study report (CSR). Additional exploratory analyses of the data may be conducted when deemed appropriate.

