### 5.8. Visit Windows

For table and figure summaries of the DB period, all data will be tabulated and analyzed per the evaluation visit as recorded on the electronic case report forms (eCRF) even if the assessment is outside of window.

For table and figure summaries of the during lumasiran treatment, the data collected at study visits during the extension period will be re-mapped for the patients randomized to placebo to reflect the visit relative to the first dose of lumasiran (e.g. Month 7 re-mapped to Month 1), Month 8 re-mapped to Month 2, etc.).

Unless otherwise specified, data collected at an unscheduled visit will be included in by patient listings and/or spaghetti plot figures, but no assignment of the scheduled visit will be made for the purposes of summary tabulations. However, unscheduled study visits will be used in the calculation of baseline values and for the any categorical shift tables (e.g. shift from baseline to worst post-baseline value).

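### The 84-day cut-off in SAP 5.2 equals the nominal Month 57 to Month 60 gap, so in-window end-of-study values can drop out of the by-visit lumasiran-treatment tables

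*SAP*

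**What the plan says.** SAP 5.2 (General Methods) treats lumasiran treatment as one continuous period. Both safety and efficacy summaries take in "any assessment collected on or after the first dose until 84 days after the last dose of lumasiran", and no tolerance is given.

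Protocol 3.1 fixes the end of dosing: "patients will receive their last dose of lumasiran at Month 57". Protocol Table 2 puts Month 57 at Day 1597 and Month 60 at Day 1681, each ±28 days, with no dose at Month 60. The SAP was written against "Amendment 2 dated 19 March 2019". The Amendment 3 summary then says of Table 2 that "the visit window was changed to" ±28 days, from ±14.

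SAP 5.8 has a rule that would keep late visits, but only for the double-blind period: those data are "analyzed per the evaluation visit as recorded on the electronic case report forms (eCRF) even if the assessment is outside of window". For lumasiran-treatment summaries it only re-aligns the placebo arm's visits ("Month 7 re-mapped to Month 1", and so on).

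At earlier open-label visits, Table 2 gives dosing as "every 84 [±28] days", and its notes add: "Assessments are to be performed prior to dosing, where applicable".

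**The concern.** A cut-off equal to the planned interval has no slack. A patient who follows the protocol throughout but comes for Month 60 one day beyond the nominal gap falls outside the period. Month 57 cannot stand in, because Table 2 schedules only dosing and a pregnancy test there, apart from the items recorded continuously. In the by-visit tables the patient's last value then goes back to Month 54, or to Month 48 for ECG and renal ultrasound.

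The rule also does not act as a limit on time since the preceding dose. A pre-dose value at an earlier open-label visit may be just as late, yet it is kept because another dose follows. Whether an end-of-study value appears therefore depends on visit timing within limits that the protocol allows. What is at stake is how complete and how readable the last visit is in the long-term tables.

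**Working it through.** **Inputs.** Month 57 = Day 1597 and Month 60 = Day 1681 (Protocol Table 2). Windows are ±14 days (Amendment 2) and ±28 days (current). Urine is collected within 14 days before the visit, and one repeat is allowed within ±14 days of the visit (Protocol Tables 2 and 7). The cut-off is 84 days (SAP 5.2).

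**Nominal gap.** 1681 − 1597 = 84 days, the same as the cut-off.

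**In-window gap.** Let d be the offset of the Month 57 dose and v the offset of the Month 60 visit. The gap is 84 + v − d, and the value is excluded when v > d.
- Largest gap, ±14: 84 + 14 + 14 = 112 days.
- Largest gap, ±28: 84 + 28 + 28 = 140 days, which is 140 − 84 = 56 days past the cut-off.
- Repeat urine, current windows: 140 + 14 = 154 days, which is 154 − 84 = 70 days past it.

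**Dose on its nominal day (d = 0).** For clinic measures, 14 of 29 allowed Month 60 days lie beyond day 84 under ±14, and 28 of 57 under ±28.

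**Both visits vary (assumption: independent, uniform over whole days).** With N days in the window, P(v > d) = (N − 1)/(2N). For urine with a lag of L days before the visit, the condition is v − L > d.

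| Measure | ±14 | ±28 |
|---|---|---|
| Clinic measures | 28/58 = 48.3% | 56/114 = 49.1% |
| Urine, lag uniform on 0 to 14 days | 28.6% | 38.0% |
| Urine, lag exactly 14 days | 105/841 = 12.5% | 903/3249 = 27.8% |

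The last row is a lower bound for urine, since it takes the earliest allowed collection day. A repeat collected after the visit would be later still.

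**Earlier visits.** Month 15 pre-dose value against the Month 12 dose: (421 + 28) − (337 − 28) = 140 days. It is kept, since it precedes the last dose.

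**Where an affected patient ends.** Month 30 = 757 + 84 = Day 841. Month 48 = 841 + 3 × 168 = Day 1345. Month 54 = 1345 + 168 = Day 1513. The last tabulated value is therefore 1681 − 1513 = 168 days before the nominal Month 60 for laboratory tests, eGFR, vital signs and quality of life. For ECG and ultrasound it is 1681 − 1345 = 336 days before.

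**Tests.** SAP 7.2 lists signed-rank timepoints that include Month 54 but not Month 60. For placebo/lumasiran patients, protocol Month 60 is re-mapped to 60 − 6 = Month 54. At 2:1 among 30 patients that is about 10 people. Their Month 54 values face the cut-off, while those of lumasiran/lumasiran patients are pre-dose and kept.

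**The case against.** The strongest defence is that 84 days is one dosing interval, chosen deliberately and used throughout: for treatment-emergent adverse events (SAP 7.7), for exposure (SAP 6.5) and for double-blind safety data of patients not dosed in the extension (SAP 5.2). Relaxing it for Month 60 creates a mismatch. An ALT value on day 100 would appear in the by-visit table, while a hepatic event starting that day would not be treatment-emergent. This stands as a cost of the change. It does not remove the point, since double-blind efficacy in SAP 5.2 already follows a visit rule.

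A second argument is that earlier late values are kept simply because dosing continues. That is right as a matter of definition. A reader might infer from the contrast that the 84-day definition is itself faulty, but the documents do not support that. They show only that the definition does not limit time since the preceding dose. Also, the stated dosing interval read alone gives 84 + 28 = 112 days. The 140 days come from combining the fixed-day windows of two visits.

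Third, any allowance treats completers differently from patients who stop early. That is true, but Month 60 is a planned visit for patients treated to Month 57, whereas off-schedule follow-up is not.

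Fourth, a later SAP version may address Amendment 3 and the pandemic. It may, but the gap already exists under the ±14-day window on which this SAP was based.

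**Conclusion.** The point holds, at low weight. That an in-window Month 60 value can be excluded follows from the stated days and windows, with no assumption beyond reading the last dose as the final dose.

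The effect is narrow. The primary and hierarchical analyses end at Month 6, time at threshold stops at 36 months on lumasiran, and adverse event analyses are unchanged. The only test touched is the signed-rank test at re-mapped Month 54 for placebo/lumasiran patients, outside the hierarchy. Listings, the selected-laboratory outputs across the study (SAP 7.7.2) and a subset of whole-study Full Analysis Set efficacy tables (SAP 5.2) keep the values. That subset is named for percent change in urinary oxalate (SAP 7.2) but is not fully listed, so it cannot be relied on for eGFR, ultrasound or quality of life. Worst-value outputs can be read either way.

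A reader might infer that about half of the patients lose their Month 60 data, or that the long-term results are undermined. Neither is supported. The 48% to 49% follows from assuming independent, uniform offsets. The documents give no visit dates and no retention to Month 60. If sites book Month 60 exactly 84 days after the actual dose, no clinic value is late. And the values leave one set of descriptive tables, not the report.

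**What to change.** Keep the 84-day limit for adverse events, exposure, and unscheduled, early-termination and safety follow-up data. Add to SAP 5.2 or 5.8: scheduled Month 60/EOS assessments of patients dosed at Month 57 are included, under their eCRF visit, in the by-visit lumasiran-treatment summaries if collected within the protocol's window for that assessment, including the repeat-urine window of Protocol Table 7. Values more than 84 days after the last dose are flagged. Set no separate day cap, because a cap at 140 days would drop compliant repeat urine collections, which can reach day 154. Assessments made under the pandemic delay allowances (up to 7 months for ECG and ultrasound, up to 4 months for questionnaires and surveys) stay outside the on-treatment label.

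The cost is one sentence, one flag variable and one footnote. Some included values will lie beyond one dosing interval, by up to 56 days for clinic measures and up to 70 days for a repeat urine collection. By-visit laboratory, ECG and vital-sign tables will then extend past the 84-day limit for treatment-emergent adverse events, and the footnote should say so.
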